### **10.2 Interaction with Participants' Healthcare Providers**

At the beginning of the study, we will ask participants for permission to contact their healthcare providers. With the participant's permission, a letter will be sent to notify the participant's healthcare provider treating their diabetes of their involvement in the study, and the conditions under which they will be contacted. As detailed below, we will contact the participant's healthcare provider treating their diabetes to inform them of diabetes medication changes. We may also contact their healthcare providers for urgent medical issues that may arise during the study.

## 10.3 Risks

### ***Risks of Questionnaires, Health History, and Anthropometric Measures***

These procedures are routine in clinical research and often clinical practice, and do not pose any significant physical risk. As with all medical information, there is always the risk of psychological distress if personal health information (PHI) is not kept confidential according to the wishes of the participant. In order to minimize this risk, data will be stored in HIPAA-compliant password-protected databases, and written information will be stored in locked files or file-rooms when not attended by research personnel. Data are collected by professional staff who are trained to perform these procedures according to detailed study protocols. The results of clinically study tests will be provided to the patient and treating sources consistent with HIPAA guidelines. Data are used only in aggregate, and no identifying characteristics of individuals will be published or presented.

### ***Risks of Phlebotomy***

Blood will be drawn at multiple time points during the study. Risks of phlebotomy include bleeding, swelling, bruising, vasovagal syncope, and pain. The likelihood of bleeding, pain, and/or bruising is high, but this risk is not serious. The risk of vasovagal syncope is low. These are all risks that exist in the course of routine medical care. To minimize risks, blood will be drawn using aseptic technique by trained staff.

### ***Risks of the Intervention***

The diet interventions follow dietary patterns of a typical American diet or similar to a healthy diet recommended for the treatment of high BP. The diet interventions have minimal risks; specific risks related to changes in BP, blood glucose, and potassium levels are discussed below in detail.

#### Discomforts Due to Change in Diet

Participants may experience some bloating and other minor gastrointestinal (GI) discomfort related to the high fruit, dairy, and fiber content of the intervention diets. It has been our experience that GI discomfort is generally minor and resolves soon after changes in diet. For those persons with lactose intolerance, we provide lactase. Participants are monitored for reactions to the diets and, if necessary, the diet can be modified or terminated. Additionally, because the study diets include nuts and seeds, there is a small risk of dental issues (e.g., chipped tooth or broken crown).

#### Risk of Changes in Blood Pressure

We anticipate that the intervention will affect participants' BP, specifically by decreasing BP in the DASH4D and lower sodium diets. However, for many participants, even the comparison diet with higher sodium might be an improvement compared to their usual diet.

#### *Elevated Blood Pressure (Escape Levels)*

In this trial, we will implement safety procedures and BP escape criteria, below, that were developed and implemented in our prior feeding studies (DASH, DASH-Sodium, OmniHeart, and OmniCarb). These safety procedures start with regular monitoring of BP.

For high BP values that do occur, we will implement BP escape levels, i.e., values at which participants will be referred for medical care. Two escape levels of BP are applied in this trial:

- 1) Escape Level #1: systolic BP >180 mmHg or diastolic BP >110 mmHg → refer for medical care
- 2) Escape Level #2: systolic BP 171-180 mmHg or diastolic BP 106-110 mmHg → repeat BP within 7 days, and if it also is in or above this range, refer for medical care

For participants meeting BP escape levels and referred for medical care, participants will not be withdrawn automatically from the study, given the well-known variability of blood pressure and the phenomenon of regression-to-the-mean. The decision regarding whether a participant should continue in or be withdrawn from the study will be left up to the participant's healthcare provider and/or the study clinician based on safety concerns. These safety procedures and approaches to decision-making are identical to those used successfully in our prior feeding studies.

### *Low Blood Pressure Reading*

The diets being tested have been shown to lower BP in the general population. When combined with anti-hypertensive medications, the dietary interventions being studied in DASH4D might further lower blood pressure, which is often asymptomatic and which, long-term, has been shown to reduce the risk of cardiovascular and kidney disease. Still, some persons might experience symptoms, such as lightheadedness, and other problems (abnormal laboratory tests). Assessment of low BP readings is complicated because BP readings are exceedingly variable, such that frequent monitoring will detect low readings without clinical consequence.

In this context, we will identify randomized participants with low readings, defined by a systolic blood pressure < 90 mmHg. If the average of the triplicate set of systolic BP readings on a given day is < 90 mmHg, the BP form will flag completion of the Hypotension Event form. Staff will ask the participant if he/she is currently feeling lightheaded or dizzy. If yes, staff will contact a study clinician for guidance while the participant is at the clinic; if no, a study clinician will receive an automatic alert from REDCap and will contact the participant within 2 days to assess symptoms of low BP and any possible explanations for the low reading. Repeat BP readings will be obtained within 8 days (or sooner, if appropriate). If the BP remains < 90 mmHg or the participant is determined to be at risk of low blood pressure, the participant will be advised to see their health care provider responsible for treating their BP for evaluation and possible adjustment of anti-hypertensive medications, or, with permission, the study clinician will directly contact the participant's health care provider.

### Risk of Changes in Blood Glucose

It is possible that diet interventions will cause changes in blood glucose. However, we expect changes in blood glucose due to the diet interventions to be small, because all diets will be isocaloric, maintaining participants' caloric intake prior to the study. The primary concern is the risk of hypoglycemia for participants using certain diabetes medications. To minimize the risk of hypoglycemia, individuals using multiple daily insulin injections and those with a history of severe or hospitalized hypoglycemia within the past 12 months are excluded.

Participants will be considered at-risk for hypoglycemia if they are using diabetes medications that are known to cause hypoglycemia: insulin, sulfonylureas, or meglitinides. For participants at-risk for hypoglycemia, we will implement a protocol to prevent and manage hypoglycemic

events, which was adapted from the hypoglycemia protocol used successfully in the Look AHEAD trial. This protocol will be used as a general guide; study clinicians will use their clinical judgment to modify these recommendations for specific participant circumstances. All study procedures to prevent hypoglycemia exist in the course of routine medical care for patients with diabetes.

#### *Hypoglycemia Prevention Education*

Participants at-risk for hypoglycemia will be educated on hypoglycemia prevention, including the risks of hypoglycemia, hypoglycemia symptoms, monitoring, and management. Participants will be instructed to check and record their blood glucose if any hypoglycemic symptoms occur. Participants will be instructed to carry a small amount of carbohydrate (e.g., glucose tablets or hard candy) in the event that they experience hypoglycemia.

#### *Hypoglycemia Risk Assessment by Study Clinician*

Prior to the intervention period, participants at-risk for hypoglycemia will meet with a study clinician, either in-person or by phone, to 1) assess the participant's risk for hypoglycemia during the intervention period, and 2) create a blood glucose self-monitoring plan for the intervention period.

- 1) **Assessing risk for hypoglycemia** - The study clinician will review the participant's recent home glucose readings and history of hypoglycemic events and symptoms, including any history of hypoglycemia precipitated by changes in diet. If the study clinician determines a participant is at high risk of having hypoglycemic events during the intervention period or may benefit from modifying their diabetes treatment prior to starting the intervention, the study clinician will recommend diabetes medication adjustments (as per **Figure 2** on management of hypoglycemia below) and contact the participant's healthcare provider.
- 2) **Creating a glucose self-monitoring plan** - The study clinician will review the participant's current glucose self-monitoring practices and recommend whether their self-monitoring should be increased during the intervention period. Participants at risk for hypoglycemia will be required, at minimum, to check a fasting blood glucose two times per week and also with any symptoms that could suggest hypoglycemia or hyperglycemia. Participants who are instructed to increase their glucose self-monitoring during the intervention period will be provided with funds to offset the cost of glucose testing supplies, if needed.

[figure not shown]
#### *Blood Glucose Self-Monitoring During the Intervention*

Participants who are instructed to monitor blood glucose will be given a blood glucose diary form and instructed to record the date, time, and blood glucose values, and any symptoms that could suggest hypoglycemia or hyperglycemia. Blood glucose diary forms will be collected weekly and reviewed by the study clinician on a weekly basis. The study clinician will be notified if there are any blood glucose values <100 mg/dL or >300 mg/dL, or for other blood glucose concerns at the discretion of study staff.

### *Diabetes Medication Adjustment for Hypoglycemia*

We will use the following medication adjustment protocol (**Figure 2**) adapted from the Look AHEAD trial and guidelines from the ADA to modify medications in response to hypoglycemic events, if they occur.

**Figure 2. Medication Adjustment Protocol for Hypoglycemia.**

Severe hypoglycemia is defined as an event requiring the assistance of another person to actively administer carbohydrates, glucagon, or take other corrective actions. If a hypoglycemic event occurs, a study clinician will contact the participant to discuss precipitants (such as skipping a meal), and may recommend behavioral interventions prior to medication change, if appropriate. The participant's healthcare provider treating their diabetes will be notified of any changes in diabetes medications. If frequent or severe hypoglycemic events occur, the frequency of the participant's blood glucose self-monitoring may be increased.

### *Management of Hypoglycemic Episodes by Study Staff*

Study staff interacting with participants will be trained in the basic management of hypoglycemic events including recognizing hypoglycemia symptoms, safe blood glucose ranges, and provision of an appropriate carbohydrate snack. A study physician will be available on-site or by phone at all times to assist with hypoglycemia or other medical issues.

### *Returning Diabetes Medications to Baseline Levels*

Participants whose diabetes medications were reduced during the study period due to hypoglycemia will be instructed to continue the glucose self-monitoring plan instituted during the intervention period for two weeks following the end of the intervention. If they have no blood glucose values <70 mg/dL and two or fewer blood glucose <100 mg/dL per week, increasing their diabetes medications to pre-intervention levels will be considered. Subsequently, the participant will be informed that their healthcare provider should resume

management of their diabetes medications. The participant's healthcare provider will be informed of their diabetes medication regimen at the end of the study.

### *Risk of Hyperglycemia*

The study intervention is not anticipated to increase the risk of hyperglycemia because all study diets are isocaloric and follow the macronutrient balance of a typical American diet. If a participant develops substantial hyperglycemia (blood glucose >350 mg/dL) or hyperglycemic symptoms, the study clinician will inform the participant's healthcare provider. Increases in diabetes medications will be performed by the participants' healthcare provider.

### Risk of Changes in Potassium Level

The intervention diet is a DASH-style diet which is higher in potassium than a typical American diet, but within the range of recommended healthy eating patterns. In a general, healthy population, a DASH-style diet should not increase blood potassium levels outside the normal range. As such, previous studies of the DASH diet and similar dietary interventions have not monitored potassium levels during the intervention.

Unlike these previous studies, this study includes some individuals who may be at a higher risk for hyperkalemia: those with chronic kidney disease and those who are using certain medications that raise potassium levels. Even among these individuals, there is a low risk of clinically significant hyperkalemia because: (1) we will exclude individuals with a history of hyperkalemia, or with elevated potassium levels during screening, (2) renal potassium excretion is not substantially impaired until the GFR is severely decreased ( $<20$  mL/min/1.73 m^2), and we will exclude those with eGFR  $<30$ , (3) hyperkalemia as an adverse effect of medications is uncommon, even among individuals with chronic kidney disease, (4) in a feeding study enrolling 29 adults with eGFR  $<60$  mL/min/1.73 m^2 who were randomized to a 4-week dietary intervention with potassium level of 3900 mg/day, there were two confirmed cases of hyperkalemia (and both were taking medications or combinations of medications that are exclusions in this trial).

To mitigate the risk of hyperkalemia during this study, we will implement a protocol for potassium monitoring and management of hyperkalemia in at-risk participants. In this trial, participants considered at-risk for hyperkalemia will be those with chronic kidney disease stage 3 or greater (eGFR  $<60$  mL/min/1.73 m^2), or using aldosterone antagonists (spironolactone or eplerenone) which are associated with increased risk of hyperkalemia in clinical trials. We will not consider participants to be at-risk if they are using medications which cause only minimal elevations in potassium and rarely cause clinically significant hyperkalemia among individuals with GFR  $>60$ , such as beta blockers, ACE inhibitor and angiotensin receptor blockers. Those trial participants who do not meet our 'at risk' criteria for hyperkalemia will not undergo potassium monitoring during the intervention period.

[figure not shown]

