**Table 1. DASH4D Eligibility Criteria.**

Inclusion Criteria

▪ Age 18 or older

▪ Diabetes Mellitus Type 2 defined by:

▪ HbA1c <math>\geq 6.5\%</math>, or

▪ Treatment of diabetes with diabetes medication(s)

▪ Baseline systolic BP of 120-159 mmHg (based on average across 3 screening visits)

▪ Baseline diastolic BP <100 mmHg (based on average across 3 screening visits)

▪ Willing and able to eat on site for one meal per day, 3 days per week, and eat only and all food provided as part of the study diets during the controlled feeding periods (run-in and four 5-week feeding periods). Note that actual frequency of on-site dining may be fewer than 3 days per week due to COVID-related restrictions, but participants will still need to be on site to pick up food and be weighed 3 days per week, and will still be expected to have meals monitored (in-person or remotely) for one meal per day, 3 days per week.

▪ Willing and able to complete required measurement procedures

▪ Have access to a mobile device or computer with video conferencing capabilities, or be willing to use a device for video conferencing provided by the study

Exclusion Criteria

▪ Laboratory Exclusions

▪ Serum potassium <math>\geq 5.2</math> mmol/L or <math><3.5</math> mmol/L

▪ Estimated GFR <math><30</math> mL/min/1.73m^2 by commercial lab result (note that prior to 7/12/22, the lab was using the race-based CKD Epi equation, and on/after 7/12/22, the lab switched to using the CKD-Epi 2021 equation, which does not provide different estimated GFR by race)

▪ HbA1c <math>>9.0\%</math>

▪ Medication Exclusions

▪ Unstable dose (i.e., change in the 2 months prior to screening or prior to randomization) of any of the following:

▪ Anti-hypertensive medications

▪ Sodium-glucose co-transporter 2 (SGLT2) inhibitors or glucagon-like

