
 
peptide-1 (GLP-1) receptor agonists
 
▪ Stimulants, including oral medications for asthma or chronic obstructive pulmonary disease (COPD)
 
▪ Hormone replacement therapy or thyroid hormone
 
▪ Weight-increasing psychotropic agents 
 
• Antipsychotic agents
 
• Lithium
 
• Mirtazapine
 
 
 
▪ Use of any of the following medications: 
 
▪ Potassium supplementation in any form, including a multivitamin or electrolyte drink mix, with a dose >99 mg/day, which is the allowable amount in over-the-counter products
 
▪ Prandial or short-acting insulin
 
▪ GLP-1 receptor agonist if on weight loss dose
 
▪ Warfarin (Coumadin)
 
▪ Chronic oral corticosteroid (intermittent use is okay)
 
▪ Weight loss medications
 
▪ Tirzepatide (Mounjaro™)
 
 
 
▪ Unwillingness to keep same dose of vitamin, mineral, and botanical supplements
 
▪ Any medication not compatible with participation as determined by the investigators
 

 
▪ Medical History Exclusions 
 
▪ Type 1 diabetes
 
▪ Hypoglycemia requiring hospitalization or the assistance of another person in the last 12 months
 
▪ Active CVD or any event in the prior 6 months, including coronary artery bypass grafting (CABG), percutaneous transluminal coronary angioplasty (PTCA), myocardial infarction (MI), cerebrovascular accident (CVA), or congestive heart failure (CHF) exacerbation requiring hospital admission
 
▪ Cancer diagnosis or treatment in the last 2 years (benign tumors or non-melanoma skin cancer or localized breast or prostate cancer not requiring chemotherapy is acceptable)
 
▪ Active inflammatory bowel disease, bowel resection, malabsorptive syndrome, pancreatitis (episode within past year), history of Roux-en-Y gastric bypass, or history of other bariatric surgery that limits food intake volume or that requires a specific diet plan
 
▪ Pregnancy or lactation or planned pregnancy
 
▪ Any emergency department (ED) visit for asthma or COPD in the last 6 months
 
▪ Any other serious illness or condition not compatible with participation as determined by the investigators
 
 
 

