### **10.1 Overview**

The trial has minimal risks. Still, participant safety is a high priority, and accordingly, we will monitor safety as described in this section. One aspect of this monitoring is to evaluate potential participants during the screening process to determine whether it is safe for them to participate in the interventions. A second aspect is monitoring the safety of enrolled participants. If a participant develops a medical problem, the safety of continuing in the study will be ascertained by a study clinician or designated safety officer, in consultation with the participant's healthcare provider if appropriate.

Substantial effort has been made to identify and minimize potential risks. For instance, those persons with a history of severe hypoglycemia within the past 12 months, with significant kidney disease, or on unstable doses of hypertension or diabetes medications are excluded. We also exclude persons with systolic BP  $\geq 160$  mmHg and/or diastolic BP  $\geq 100$  mmHg. Such persons are informed of their elevated BP level and advised to consult with their physician. Likewise, persons with active CVD or recent cardiovascular events, eGFR  $< 30$  mL/min, a history of high potassium levels, or baseline serum potassium  $\geq 5.2$  or  $< 3.5$  mmol/L are excluded. See 6.2 Eligibility Criteria for full details on exclusions.

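### Protocol 10.1 and 10.3 say people with past hyperkalemia are excluded, but neither Table 1 nor the at-risk definition mentions potassium history, so such a person can enter without the week-1 potassium check

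*Combined protocol and SAP*

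**What the plan says.** Protocol 10.3, under the risk of changes in potassium level, gives four numbered reasons why clinically significant hyperkalemia should be uncommon. Reason (1) is that "we will exclude individuals with a history of hyperkalemia, or with elevated potassium levels during screening". Section 10.1 makes the same statement, listing among the excluded those with "a history of high potassium levels, or baseline serum potassium" outside the stated limits. It ends by sending the reader to the eligibility section: "See 6.2 Eligibility Criteria for full details on exclusions".

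Reason (4) reports a feeding study of 29 adults with eGFR below 60, given 3900 mg/day of potassium for 4 weeks, in which two had confirmed hyperkalemia. It sets those two cases aside because "both were taking medications or combinations of medications that are exclusions in this trial".

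Section 10.3 then defines who is at risk and so has potassium checked at the end of week 1 of each period: people with eGFR below 60, or those "using aldosterone antagonists (spironolactone or eplerenone) which are associated with increased risk of hyperkalemia in clinical trials". Everyone has potassium measured in the fasting panel at the end of each feeding period.

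On drug stability, 10.1 says that people "on unstable doses of hypertension or diabetes medications are excluded".

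**The concern.** The safety argument relies on an exclusion that the table of criteria does not contain. Table 1 is presented in 6.2 as the study's eligibility criteria, and section 9 describes a computer check before randomization that all of them are met. An exclusion that appears only in the risk narrative has no stated route into that check.

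The at-risk definition has the same gap. If potassium history were a Table 1 exclusion, leaving it out of the at-risk definition would do no harm, because nobody with that history would be enrolled. If it were an at-risk criterion, leaving it out of Table 1 would matter less, because those people would be checked early. It is in neither place. Two of the four diets target 3900 mg/day of potassium at 2000 kcal (Table 2), so the early check has a purpose for someone with this history.

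**Working it through.** No design figure is involved, so the check is a comparison of the sections.

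| Statement in the safety sections | Entry in Table 1 (6.2) | Result |
|---|---|---|
| History of high potassium excluded (10.1; 10.3 reason 1) | None | Not found |
| Elevated screening potassium excluded (10.1; 10.3 reason 1) | ≥5.2 mmol/L; also <3.5 mmol/L | Agrees |
| eGFR below 30 excluded (10.1; 10.3 reason 2) | eGFR below 30 | Agrees |
| Drugs or drug combinations of the two cited cases excluded (10.3 reason 4) | Only item aimed at potassium: "Potassium supplementation in any form, including a multivitamin or electrolyte drink mix", above 99 mg/day; no combination listed | Cannot be traced |
| Unstable doses of diabetes medications excluded (10.1) | Among glucose-lowering drugs, SGLT2 inhibitors and GLP-1 receptor agonists only | Table 1 is narrower |

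**Is the missing history item only shorthand?** The other specific exclusions in the same part of 10.1 can be found in Table 1: severe hypoglycemia in the past 12 months, active or recent cardiovascular disease, the eGFR limit, the potassium limits and the blood pressure limits. Potassium history is the one with no counterpart at all.

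**Tracing one person through the rules.** Take someone with past hyperkalemia, screening potassium of at least 3.5 and below 5.2, eGFR of at least 60, and no aldosterone antagonist.

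1. Table 1: no specific exclusion applies.
2. At-risk definition: neither criterion is met.
3. Week-1 check: not done, because 10.3 and footnote 6 of Table 3 restrict it to at-risk participants.
4. First scheduled potassium on diet: the fasting panel in weeks 4-5.
5. If that value is high, the at-risk algorithm does not apply. Section 10.3 provides a recheck and then leaves action to the study clinician.

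**Timing.** Footnote 6 puts the early check at about week 2 day 1, which is day 3·7 − 20 + 7 = 8, or more simply 7 + 1 = 8. Week 4 day 1 is day 3 × 7 + 1 = 22, and the end of week 5 is day 5 × 7 = 35. The first value therefore comes 22 − 8 = 14 to 35 − 8 = 27 days later than it would for an at-risk participant. This recurs in each period.

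**Medication phrase.** Section 10.3 does not name the drugs the two cases took. Outside the supplement item, Table 1 names no drug as excluded for raising potassium. Section 10.3 treats users of aldosterone antagonists as enrollable with monitoring, and users of beta blockers, ACE inhibitors and angiotensin receptor blockers as enrollable without it.

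**Dose stability.** The Table 1 entry begins "Sodium-glucose co-transporter 2 (SGLT2) inhibitors or glucagon-like" and goes on to GLP-1 receptor agonists. Other glucose-lowering classes, such as sulfonylureas, are not in the unstable-dose list. This has no effect on potassium monitoring.

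**A related wording conflict.** Section 10.3 says participants not at risk have no potassium monitoring during the intervention period, and then says all participants have an end-of-period potassium. These sentences should be aligned in the same edit.

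**The case against.** The strongest reply is that such a person would probably be caught. A study clinician reviews the medical history and medications at or after the first screening visit. Table 1 has catch-all items for incompatible conditions, incompatible medications and investigator discretion. Potassium is measured at the second screening visit and again in the fasting panel at the third. Sections 10.1 and 10.3 are themselves protocol text, and the screening forms, which may ask about potassium history, are not among the documents. All of this lowers the chance of harm. It does not remove the contradiction: the catch-all items allow exclusion without requiring it, an in-range value says nothing about history, and 10.1 names 6.2 as the full list.

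Three stronger readings are tempting, and the documents do not support them.

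- A reader might use the cited study, 2/29 = 6.9% (exact 95% interval 0.8% to 22.8%), as the risk in the unchecked person. Those adults had eGFR below 60, so here they would be at risk and would have the week-1 check. The figure does not describe people with eGFR of at least 60.
- A reader might conclude that reason (4) is shown to be false. It is only untraceable. The drugs are not named; a potassium supplement, which Table 1 does exclude, may have been involved, and the medication catch-all could cover others. Enrolling aldosterone-antagonist users is not itself a contradiction, because 10.3 says openly that some participants take drugs that raise potassium.
- A reader might think all three mismatches lead to a missed check. Only the history mismatch does. Aldosterone-antagonist users are checked at week 1, and diabetes-drug dose stability is a separate matter.

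**Conclusion.** The plan is wrong as written on one point that bears on participant safety. Past hyperkalemia is declared an exclusion in 10.1 and 10.3 and used as part of a low-risk argument, but it is absent from Table 1 and from the at-risk definition. The people affected are those with past hyperkalemia, in-range screening potassium, eGFR of at least 60 and no aldosterone antagonist. For them the first on-diet potassium comes 14 to 27 days after the time of the week-1 check. Their number and their risk cannot be estimated from the documents.

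The medication phrase in reason (4) needs a source in the criteria or a correction. The dose-stability wording in 10.1 is a lesser mismatch; it touches the glycemia outcomes at most, and those are neither primary nor secondary.

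The conclusion assumes that Table 1 is the operative list, as 6.2 and 10.1 indicate, and that no screening form outside these documents already applies the history exclusion.

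**What to change.** Reconcile Table 1 with 10.1 and the potassium part of 10.3, so that the eligibility table, the at-risk definition and the risk argument state the same criteria. Carry the agreed list into the pre-randomization eligibility check. If enrollment has finished, state which criteria were actually applied, so that the safety results are read against the right population.

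If the investigators keep Table 1 as it stands, three phrases need correcting: the history phrase in reason (1) and its counterpart in 10.1, the parenthesis about excluded medications in reason (4), and the diabetes-drug dose-stability wording in 10.1. Reasons (1) and (4) should not be deleted whole. Reason (1) also contains the screening-potassium exclusion, which is in Table 1, and reason (4) is where the two hyperkalemia cases are disclosed.

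Which clinical rule applies is for the investigators. The cost is protocol wording and, if a history criterion is adopted and not already asked about, one screening item.
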